## **10.10.** Maximum Blood Volume

The maximum amount of blood collected from each subject over the duration of the study, including planned pharmacokinetic, biomarkers, and clinical laboratory samples will not exceed 240 mL. Repeat or unscheduled samples may be taken for safety reasons or for technical issues with the samples.

## **10.11. Procedures for Overdose**

Overdose is not expected as study treatment will be administered in a highly controlled environment by qualified designees at the study centers. The Sponsor does not recommend specific treatment for an overdose; there is no known antidote to temanogrel. After an overdose or suspected overdose, subjects should be monitored for adverse events.

If a subject receives a dose in excess of the instructed dose (eg, due to pharmacy error) and if symptoms are present, the Investigator or designee should contact the Medical Monitor immediately. In the absence of associated adverse events as assessed per the clinical judgement of the Investigator, no further action is required. Overdoses must be documented as protocol deviations.

## 11. PLANNED STATISTICAL METHODS

## **11.1. General Considerations**

Details regarding the statistical analyses will be provided in the Statistical Analysis Plan (SAP), which will be finalized prior to breaking the blind for the Stage A interim analysis.

Continuous variables will be summarized using the number of observations, mean, standard deviation (SD), median, minimum, and maximum. Categorical variables will be summarized using frequency counts and percentages.

Pairwise comparisons of each temanogrel treatment group compared to placebo will be conducted. In addition, analyses of the pooled temanogrel treatment groups compared to placebo will be conducted.

Where statistical assumptions (eg, normality, first-order carry effects) are not met, alternative approaches will be evaluated (eg, nonparametric analysis, log transformation). All statistical tests for efficacy parameters will be performed at the 0.05 significance level (2-sided).

Efficacy data will be analyzed by randomized treatment, while safety data will be analyzed by actual treatment.

Details regarding the statistical analyses will be provided in the SAP.

## **11.2.** Determination of Sample Size

Approximately 24 subjects are planned to be randomized in Stage A, which is sufficient to achieve at least 80% power to detect a treatment effect of 16.6% from placebo for change in digital blood flow based on rewarming AUC (°C, assessed with IR thermography) during the 30 minutes following a cold challenge for each of the 2 temanogrel treatments based on a difference of means test for a 3-period, 3-treatment crossover design with a significance level 0.05 (2-sided). The test assumes the temanogrel treatment group mean of 365, placebo group mean of 313, and an SD of the difference in temanogrel treatment and placebo group means of 86. In addition, with 24 subjects there is at least 80% power to detect a treatment effect of 23.5% from placebo for change in digital blood flow based on reperfusion AUC (pu, assessed with LSCI) during the 30 minutes following a cold challenge for each of the 2 temanogrel treatments (temanogrel treatment group mean of 24.7, placebo group mean of 20, and an SD of the difference in temanogrel treatment of 7.8). Assumptions are based on previous studies in SSc-RP utilizing these or similar methods (Herrick 2014, Wilkinson 2018,

Wise 2004). Subjects will be equally randomized (1:1:1:1:1:1 ratio) to 1 of the 6 treatment sequences (4 subjects per sequence).

Approximately 24 subjects are planned to be randomized in Stage B using the same 3-period, 3-treatment crossover design. Based on Stage A results, Stage B sample size may be modified, but not limited to, Stage A dose levels will be enriched or 2 additional temanogrel doses will be evaluated.

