for a minimum of 5 minutes before the start of imaging should be avoided. Hands should be placed at a fixed distance and angle from the thermal camera and LSCI and secured to avoid movement during imaging. Both hands will be used for digital blood flow assessments and cold challenges. Room temperature digital blood flow assessment will be performed following acclimatization for at least 20 minutes. For the cold challenge, hands will be placed in nitrile gloves (to prevent evaporative cooling) and immersed in a temperature-controlled water bath  $(15 [\pm 1]^{\circ}C)$  up to the radiocarpal joints for 1 minute ( $\pm$  3 seconds). The water temperature should be recorded at the beginning and at the end of the cold challenge. Immediately after the cold challenge, the gloves will be removed, the hands will be dried and returned to their original position on the insulating surface, and the post-cold challenge digital blood flow assessment will start 30 ( $\pm$  10) seconds after the end of the cold challenge.

ROIs on both hands will be predefined and the same ROIs will be used for analysis during all digital blood flow measurements for all subjects. Data will be presented in temperature (°C) for IR thermography or in arbitrary pu for LSCI and averaged for all ROIs. Absolute measurements (eg, room temperature values, maximum reduction/recovery) as well as dynamic assessments dependent on the characteristics of the rewarming/reperfusion curve (eg, AUC, time to 50% and 70% recovery [minimum value + (baseline value – minimum value)  $\times$  0.5 and minimum value + (baseline value – minimum value)  $\times$  0.7]) will be assessed.

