#### **11.5.1. Primary Endpoint**

- Change in digital blood flow based on:
  - Rewarming AUC (°C, assessed with IR thermography) during the 30 minutes following a cold challenge
  - Reperfusion AUC (pu, assessed with LSCI) during the 30 minutes following a cold challenge

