## 11.7. Interim Analysis

Following Stage A, unblinded analyses will be conducted to review the safety, PK, and efficacy (eg, observed treatment effect, variability of digital blood flow measures) data. Based on Stage A results, Stage B sample size may be modified, such as, but not limited to, Stage A dose levels will be enriched, or 2 additional doses will be evaluated. Full details of the safety, PK, and efficacy data interim analyses will be provided in the SAP.

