- n Room temperature digital blood flow is assessed at each Treatment Visit at Predose for 5 minutes and at Postdose for 5 minutes prior to the cold challenge.
- The cold challenge is conducted at each Treatment Visit at after Postdose room temperature (pre-cold challenge) digital blood flow assessments by immersing the hands in temperature-controlled water bath (15 [± 1]°C) for 1 minute (± 3 seconds). The post-cold challenge digital blood flow assessments will begin 30 (± 10) seconds after the completion of the cold challenge and last for 30 minutes.
- p Dosing is to occur at each Treatment Visit after completion of the Predose assessments.

q To be completed at each Treatment Visit at Postdose after completion of post-cold challenge digital blood flow assessments and blood draws.

ECG, electrocardiogram; eCRF, electronic case report form; IR, infrared; PK, pharmacokinetic

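### Are the planning means of 313 and 365 in Section 11.2 impossible for a 30-minute rewarming AUC?

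*Combined protocol and SAP*

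**What the plan says.** Section 11.2 claims at least 80% power for each temanogrel dose to detect an "effect of 16.6% from placebo for change in digital blood flow based on rewarming AUC (°C, assessed with IR thermography) during the 30 minutes" after the cold challenge. The inputs are: "The test assumes the temanogrel treatment group mean of 365, placebo group mean of 313", and an SD of 86 for the difference. For perfusion measured by LSCI the inputs are 24.7 against 20 with an SD of 7.8, an effect of 23.5%. The section attributes these assumptions to three earlier studies in SSc-RP that used the same or similar techniques.

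Section 11.5.1 lists the thermography endpoint, under a heading that calls it a change in digital blood flow, as "Rewarming AUC (°C, assessed with IR thermography) during the 30 minutes following a cold challenge". No reference level and no time unit are given.

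The procedure comes from Appendix 1 and Section 10.3.1. The challenge consists of "immersing the hands in temperature-controlled water bath (15 [± 1]°C) for 1 minute", with gloves worn against evaporative cooling. Imaging begins 30 (± 10) "seconds after the completion of the cold challenge and last for 30 minutes", in a room held at 23 ± 1°C. On the scale of the data, Section 10.3.1 says: "Data will be presented in temperature (°C) for IR thermography or in arbitrary pu for LSCI and averaged for all ROIs". It gives explicit formulas, built from the minimum and baseline values, for the 50% and 70% recovery times, but none for the AUC. It refers the analysis method to one of the studies cited in 11.2 and to separate operation manuals. Section 11.1 leaves further statistical detail to the SAP.

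**The concern.** The means look impossible when set against the procedure. If skin is never colder than the coldest permitted water and the AUC is the area under skin temperature in °C·min, its lower limit is 420. Values of 313 and 365 would mean average skin temperatures of 10.4 and 12.2°C, below the bath itself.

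If the means belong to some other quantity, the percentage is in doubt, because a percentage effect depends on where zero is placed. On a raw °C·min scale a difference of 52 would be at most 12.4% of placebo, and about 7% if the planning figures were areas above roughly 15°C. A Stage A result exactly on plan could then be reported as under half the stated target. Section 11.7 has the sponsor review "efficacy (eg, observed treatment effect, variability of digital blood flow measures) data" before settling Stage B, and Section 11.1 allows a log transformation, which works on ratios and so also depends on the zero point. If the source figures came from a window shorter than 30 minutes, the claimed power would not carry over to the primary endpoint.

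**Working it through.** **Inputs.** Section 11.2: means 365 and 313, SD of the difference 86, n = 24, two-sided 0.05; for LSCI 24.7, 20 and 7.8. Appendix 1: bath 14 to 16°C, imaging for 30 minutes.

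**1. The plan's own figures.**
- Relative effect: (365 − 313)/313 = 52/313 = 16.6%. For LSCI: 4.7/20 = 23.5%. Both reproduce.
- Power: the noncentrality is 52/(86/√24) = 2.96. This gives 81.0% (paired t, 23 df), 82.6% (crossover ANOVA, 44 df) or 84.2% (normal approximation). The smallest n for 80% is 24, 23 or 22 respectively.
- LSCI power by the same three methods: 80.7%, 82.3% and 83.9%.

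**2. The raw-area reading.**
- Lower limit: 14 × 30 = 420 °C·min (450 at 15°C, 480 at 16°C), assuming skin does not fall below the bath temperature.
- 313/30 = 10.4°C and 365/30 = 12.2°C, both below 14°C. A raw area in °C·min is ruled out as the planning scale.
- On that scale 52/420 = 12.4% would be the ceiling for the percentage.

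**3. An area above a reference level r over the same 30 minutes.** Mean temperature = r + AUC/30. The values of r are illustrative, since the documents give none.

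| r (°C) | Placebo mean (°C) | Temanogrel mean (°C) |
|---|---|---|
| 14 | 24.4 | 26.2 |
| 16 | 26.4 | 28.2 |
| 20 | 30.4 | 32.2 |

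The lower rows of reference values give means close to the 23 ± 1°C room and the 27°C digit temperature required at screening. The full 30-minute window and every figure in 11.2 are preserved.

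**4. Effect of a fixed reference on power.** Subtracting 30r from every AUC cancels in each within-subject difference, so 52 and 86, and hence the power, do not move. Only the percentage does. With r = 15°C the raw means would be 313 + 450 = 763 and 365 + 450 = 815, and 52/763 = 6.8% (7.1% for r = 14, 6.6% for r = 16). The ratio would be 815/763 = 1.07 in place of 365/313 = 1.17.

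**5. Use of the percentage.** Section 11.5 tests differences in least-squares means. Section 11.7 looks at observed effect and variability with no 16.6% threshold. No stated decision turns on the percentage.

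**The case for a change.** The strongest reply is that no finalised document in the file fixes the scale of a primary endpoint. Section 10.3.1 writes out formulas for two secondary recovery times and none for the primary AUC. The Note to File (Amendment 1) records that the SAP stopped at draft v0.5 and that efficacy is to be analysed separately. The choice can matter: an area above each visit's own minimum and an area above a fixed level differ by 30 °C·min for every 1°C by which treatment shifts the minimum, against a planned difference of 52. Section 11.2 also allows that its sources used similar rather than identical methods.

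This establishes that the definition is missing from the protocol text, and that much stands. It does not establish that any figure is wrong. The 12.4% ceiling and the values near 7% hold only if the endpoint is analysed as a raw area in °C·min, which the protocol never says; the printed unit is °C alone. A shorter source window is conjecture against a section that states 30 minutes. The visit-minimum problem concerns a choice the documents do not make and a shift whose size they do not give. The analysis method in 10.3.1 and the assumptions in 11.2 share a cited source, so an analyst has an obvious place to take the formula from. For LSCI the file gives no perfusion level against which 20 and 24.7 could be checked.

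**Conclusion.** No change to the plan follows. The means 313 and 365 cannot be raw 30-minute areas in °C·min, but they fit a 30-minute area above a reference level, which is a natural meaning of a rewarming AUC. On that reading 16.6%, the SD of 86, n = 24 and about 81% power all stand.

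What is left is a gap in wording: the reference level and time unit are missing from 11.2 and 11.5.1 and are left to the cited method and the operation manuals. An analyst fills that gap by using the core lab's formula and quoting the percentage on the same scale. Stage B sizing no longer arises, because enrollment was terminated.

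This conclusion assumes that the AUC analysed has the same definition as the one behind the planning figures, or differs from it only by a fixed level. The documents do not allow that to be verified, but nothing in them contradicts it.

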## 11.3. Analysis Sets

For purposes of analysis, the following populations are defined (Table 3).

Analysis Set	Description
Full Analysis Set (FAS)	The FAS will include all randomized subjects, irrespective of whether they received any study treatment.
Modified Full Analysis Set (mFAS)	The mFAS will include all randomized subjects who receive at least one dose of study treatment and have at least one baseline and post-baseline measurement.
Per Protocol Set	The Per Protocol Set will include all subjects from the FAS who receive the full dose of all 3 study treatments and are without major protocol violations that might affect the evaluation of the effect of study treatment on the primary endpoints. The violations will be predefined in the SAP and the Per Protocol Set will be specified prior to unblinding.
Pharmacokinetic Set	The Pharmacokinetic Set will include all subjects in the Safety Set with a Postdose PK measurement.
Safety Set	The Safety Set will include all randomized subjects who received at least one dose of study treatment.

Table 3:Analysis Sets

## 11.4. Missing Data

If required, imputation of missing data will be performed and details will be given in the SAP.

## 11.5. Efficacy Analyses

The primary and secondary endpoints will be analyzed using the FAS. Other important statistical considerations and sensitivity analyses will be described in the SAP.

The primary endpoints of the study are the change in digital blood flow based on rewarming/reperfusion AUC (assessed with IR thermography and LSCI, respectively) during the 30 minutes following a cold challenge. The primary analyses will be analyzed using analysis of variance (ANOVA; Williams' design) with a model that includes treatment group, sequence, and period as factors. Least square means, standard errors (SEs), and 95% confidence intervals (CIs) for the treatments and their difference will be presented together with their p-values.

Unless otherwise specified, continuous secondary endpoints will be analyzed using ANOVA (Williams' design) with a model that includes treatment group, sequence, and period as factors. Least square means, SEs, and 95% CIs for the treatments and their difference will be presented together with their p-values.

Time-to-event secondary endpoints will be displayed using Kaplan-Meier plots and analyzed with Cox regression with a model that includes treatment group, sequence, and period as factors. The hazard ratio will be presented together with 95% CIs and the p-value.

Given subjects will receive all 3 treatments in 1 of 6 possible sequences, first-order carryover effects will be evaluated to assess the extent to which the order of treatments affected primary and secondary endpoints.

Details of the analysis methods for exploratory endpoints will be described in the SAP.

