### 3.2.3. Study Design and Methodology

This study has been designed as a randomized, double-blind, placebo-controlled, crossover study to reduce patient selection and assessment bias, and account for placebo effect and inter-subject differences in digital blood flow. Non-invasive assessment of the effect on digital blood flow following a single dose of study treatment was chosen as the primary objective for this POM study to ensure a reliable and objective initial evaluation of pharmacodynamic effects in the setting of SSc-RP (Wilkinson 2018). Patient-reported outcomes (PROs) designed to evaluate the frequency, duration, and severity of Raynaud's attacks, commonly used to evaluate real-world efficacy of pharmacotherapies in this setting, have not been included as primary efficacy assessment in this study due to short treatment duration.

Exposure to cold challenge was incorporated in the study design to allow for a dynamic assessment of digital blood flow under conditions similar to a common physiological trigger responsible for Raynaud's attacks in SSc (Pauling 2012). Digital blood flow will be assessed each Treatment Visit at Predose for 5 minutes at room temperature, and at Postdose prior to cold challenge for 5 minutes at room temperature and for 30 minutes following a cold challenge. Washout Periods between Treatment Visits are defined as a minimum of 72 hours, which is a sufficient period to ensure elimination of temanogrel, and up to approximately 7 days, to accommodate feasibility of multiple study visits for the study participants. Biomarkers related to

the mechanism of action of temanogrel (plasma serotonin concentration) as well as vascular injury and endothelial dysfunction will be evaluated to explore their relationship with digital blood flow and the PD effects of temanogrel, in order to provide additional mechanistic insights.

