# Note to File (Amendment 1)

Date:	28 October 2022	
To:	TMF	
From:	PPD	
Protocol No.:	APD791-204	
Subject:	Document the status of biometrics-related documents/processes and outline plan for select post-database lock safety and efficacy analyses	
Background:	
 
On 25 August 2022, the decision was made to discontinue development of the Arena cardiovascular programs, which includes APD791 (temanogrel). Enrollment into the ongoing clinical trial APD791-204 was terminated effective immediately and study team activities were reprioritized to focus and accelerate study close-out activities. For this study, the biostatistics, data management, and statistical programming deliverables and activities are outsourced to the clinical research organization (CRO) Medpace.
 
As a result of the immediate termination, the biostatistics aspects related to finalizing documents (e.g., statistical analysis plan [SAP]) and other downstream activities are either immature and/or have not been established. These tasks would take significant time and resources by both the Arena and Medpace team to finalize, which is not feasible given the accelerated study close-out timeline, which includes the database lock (DBL) which occurred on 13 October 2022.
 
	
Final Status:	
 
Statistical Analysis Plan
 
Draft SAP (v0.5)
 
Statistical Analysis Plan: Table, Listing, and Figure (TLF) Shells
 
	
	• Draft TLF specifications (v0.2)	
	
 
CDISC Specifications and Datasets (aCRF/SDTM/ADaM)
 
aCRF (dbCRF; based on protocol amendment v3.0)
 
SDTM: Specifications and datasets by 04 November 2022
 
ADaM: Draft specifications (development not yet begun)
 
	
	
 
Statistical Analysis Plan: Table, Listing, and Figure (TLF) Programming
 
Based on Programming Specifications (v1.0 dated 11 October 2022), the listings described in "Deliverables & Analyses" section will be produced.
 
	
	
 
Define.xml
 
Development has not begun for either SDTM or ADaM Defines
 
	

[figure not shown]

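### The crossover ANOVA and Cox models list treatment, sequence and period but no subject effect or clustering adjustment, although the sample size rests on within-subject differences

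*Combined protocol and SAP*

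**What the plan says.** Section 11.5 (Efficacy Analyses) describes the primary analysis as an ANOVA, labelled Williams' design, "with a model that includes treatment group, sequence, and period as factors". It repeats the same terms for continuous secondary endpoints, and the Synopsis (Statistical Analysis) does so for both. Time-to-event secondary endpoints are to be "analyzed with Cox regression with a model that includes treatment group, sequence, and period as factors". No section names subject as a fixed or random effect, a within-subject covariance, a frailty, a subject stratum or a robust variance.

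Two other sections assume a within-subject comparison. Section 11.2 uses "an SD of the difference in temanogrel treatment and placebo group means of 86" for rewarming AUC and an SD of the difference of 7.8 for reperfusion AUC. Section 3.2.3 says that the crossover was chosen, among other reasons, to "account for placebo effect and inter-subject differences in digital blood flow".

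Section 11.1 leaves analysis details to the SAP. Note to File (Amendment 1) records that the SAP stood at draft v0.5 when the programme was discontinued and would not be finalised. It adds that efficacy will be analysed separately and is not planned for the clinical study report. The draft's text is not among the documents.

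**The concern.** In a three-period crossover each subject supplies one record per treatment, and the gain from the design comes from comparing those records within the subject. A sequence term removes differences between the six sequence means. It does not remove differences among the four subjects who share a sequence. If only the three listed terms are fitted, that variation goes into the residual against which treatment is tested.

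At stake is precision, not false positives on the treatment contrasts. Standard errors would be overstated and a real effect could be missed in a proof-of-mechanism study whose Stage A results were meant to guide Stage B doses and sample size. The sequence test would also use the wrong error term.

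The Cox model has a related gap. Its usual standard error treats all records as independent, which three records per subject are not.

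**Working it through.** **Inputs.** From Sections 11.2 and 6.4: 24 subjects, 6 sequences of 4, two-sided alpha 0.05. Rewarming AUC means are 365 and 313 (difference 52), with SD of the difference 86. Reperfusion AUC means are 24.7 and 20 (difference 4.7), with SD of the difference 7.8. The correlation ρ between a subject's visits is not given, so it is an assumption, varied from 0 to 0.8. The model further assumes normal data, one between-subject and one within-subject variance, and complete balanced data.

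**1. The plan's own figure.** SE = SD of difference / √24.
- Rewarming: 86/√24 = 17.55 and 52/17.55 = 2.96. Noncentral t power is 81.0% on 23 df (paired) and 82.6% on 44 df (crossover ANOVA with subject).
- Reperfusion: 7.8/√24 = 1.59 and 4.7/1.59 = 2.95. Power is 80.7% and 82.3%.
- Reading 86 and 7.8 as per-treatment SDs, with 24 per group compared as independent groups, gives only about 54% and 53%.

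The stated power is therefore right, and it is a within-subject figure.

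**2. Residual degrees of freedom.** There are 24 × 3 = 72 records.
- Listed terms only: 72 − 1 − 2 − 5 − 2 = 62.
- With subject: 72 − 1 − 2 − 2 − 23 = 44.
- The 18 df of difference are subjects within sequence (24 − 6).

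**3. Expected residual mean square, listed terms only.** Let σw² = (SD of difference)²/2, which is 86²/2 = 3698 for rewarming, and σb² = σw² × ρ/(1 − ρ). Then

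E(MS) = [18(σw² + 3σb²) + 44σw²]/62 = σw² × [1 + (54/62) × ρ/(1 − ρ)].

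At ρ = 0.5 the bracket is 1 + 54/62 = 1.871, so the reported SE is about 17.55 × √1.871 = 24.0. The true SE of the treatment difference is still 17.55.

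**4. Power.** A quick check at ρ = 0.5: the difference must exceed about 2.00 × 24.0 = 48.0. The chance is Φ((52 − 48.0)/17.55) = Φ(0.23), about 59%. The table averages over the sampling variation of the residual mean square, using simulated chi-square components on 18 and 44 df. The SE, CI and type I error columns are for rewarming AUC.

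| ρ (assumed) | Reported SE | 95% CI half-width | Type I error | Power, rewarming | Power, reperfusion |
|---|---|---|---|---|---|
| 0 | 17.6 | 35 | 5.0% | 83% | 83% |
| 0.2 | 19.4 | 39 | 3.1% | 77% | 77% |
| 0.3 | 20.6 | 41 | 2.3% | 73% | 73% |
| 0.5 | 24.0 | 48 | 0.9% | 59% | 59% |
| 0.7 | 30.6 | 61 | 0.15% | 33% | 32% |
| 0.8 | 37.2 | 74 | 0.02% | 14-15% | 14% |

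Power falls below 80% at a correlation just above 0.1. Simulation of whole trials on the six-sequence design gave the same pattern. With a subject term, power stayed at about 82-83%, type I error at about 5% and the half-width at about 35 for every ρ. Where the two models were compared on the same simulated data, their treatment estimates agreed to within rounding.

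**5. Cox model.** No magnitude is claimed, because the documents give no hazards or frailty variance.

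**The case against.** The strongest reply is that the literal reading is not the intended one. The ANOVA is labelled as a Williams' design, Section 11.2 uses a crossover test on the SD of the difference, and Section 3.2.3 states the within-subject purpose. Protocols often list only fixed factors and leave the error structure to the SAP. A draft SAP existed and was used for the pharmacokinetic parameters, so it may have contained the term. This is fair on intent, and it means the power loss is a consequence of following the text, not a demonstrated error in a completed analysis. It does not supply the missing term. Williams' design names a layout of sequences, the sentence then lists the factors without subject, and no final SAP exists to complete it.

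It is also fair that the loss depends on an assumed correlation, that the small type I error figures are only as exact as the assumptions, and that the ANOVA error runs in the conservative direction. However, Section 3.2.3 cites high repeatability of this same AUC for both imaging methods, which makes a correlation near zero the least plausible end of the range.

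The Cox point concerns secondary endpoints that Section 11.6 treats as exploratory. A small illustrative simulation with an assumed frailty gave model standard errors that were too large, not too small. It had convergence warnings and about 10% type I error even without frailty, so it settles nothing on size. The Cox point stands as a missing specification only.

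**Conclusion.** The concern holds. The written model does not match the sample size that it is meant to serve. The sample size itself is correct. Followed literally, the ANOVA delivers the stated 80% power only if a subject's visits are almost uncorrelated (up to about 0.1). At an assumed correlation of 0.5, rewarming power is about 59% and the 95% CI half-width about 48, against about 83% and 35 with a subject term. These figures rest on the assumed correlation range, a common variance and correlation across visits, normality, and complete data with four subjects per sequence. For positive correlation there is no inflation of type I error on the treatment contrasts, and with balanced data no change in the estimates. For the time-to-recovery endpoints, the hazard ratio's standard error has no stated basis that allows for repeated records. Because efficacy is to be analysed outside the study report and without a final SAP, Section 11.5 and the matching Synopsis text are the only visible specification, so this should be corrected.

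**What to change.** In the Synopsis and Section 11.5, state that continuous endpoints are analysed by a linear mixed model (or ANOVA) with treatment, period and sequence as fixed effects and subject nested in sequence as a random (or fixed) effect, and that sequence is tested against the subject-within-sequence stratum.

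For time to 50% and 70% recovery, choose one approach and name the hazard ratio it targets: a subject-clustered robust variance for a marginal hazard ratio, or a subject frailty for a subject-specific one.

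Since the SAP will not be finalised, put the same wording in whatever document governs the separate efficacy analysis. The cost is a sentence or two and one model term, with no new data, no new patients and no change to the 24 subjects.
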